#### 3.4.5 Severe Hypersensitivity Reactions and Flu-Like Symptoms

If hypersensitivity reaction occurs, the subject must be treated according to the best available medical practice. Subjects should be instructed to report any delayed reactions to the Investigator immediately.

For prophylaxis of flu-like symptoms, 25 mg of indomethacin or comparable nonsteroidal anti-inflammatory drug (NSAID) dose (for example, ibuprofen 600 mg, naproxen sodium 500 mg) may be administered 2 hours before and 8 hours after the start of each dose of avelumab IV infusion. Alternative treatments for fever (for example, paracetamol) may be given to subjects at the discretion of the Investigator.

#### 3.4.6 Tumor Lysis Syndrome

In addition, since avelumab can induce antibody-dependent cell-mediated cytotoxicity, there is a potential risk of tumor lysis syndrome. Should this occur, subjects should be treated per the local guidelines.

### 3.5 STUDY CALENDAR

Procedures	Screening	Baseline	Course 1				Course 2 (if indicated)			End of Treatment a	Follow-up d
			Cycle 1 Day 1	Cycle 2 Day 1	Cycle 3 Day 1	End of Course 1	Cycle 1 Day 1 o	Cycle 2 Day 1	Cycle 3 Day 1		
History and PE b	X f	X c,e	X c,e	X c	X c	X m	X c	X c	X c	X	X
Vital signs, weight, O 2 saturation	X f	X c,e	X c,e	X c	X c		X c	X c	X c	X	X
Height		X									
ECOG Performance Score	X f										
Confirmation of diagnosis	X										
NIH Advance Directives Form s		X									
CBC with differential	X c,e	X c,e	X c,e	X c	X c	X m	X c	X c	X c	X	X
Chemistry panel including: LDH, AST, ALT, ALP, T.Bili, BUN or serum urea level, creatinine, Ca, Mg, Na, K, Cl, glucose, amylase, lipase, TSH, free T4, free T3 c	X c,e	X c,e	X c,e	X c	X c	X m	X c	X c	X c	X	X
Antibody screen for Hepatitis B and C; HIV p	X p										

Procedures	Screening	Baseline	Course 1			Course 2 (if indicated)			End of Treatment a	Follow-up q,r
			Cycle 1 Day 1	Cycle 2 Day 1	Cycle 3 Day 1	End of Course 1	Cycle 1 Day 1 o	Cycle 2 Day 1		
Pregnancy test c	X c,e	X c,e	X c,e	X c	X c	X c		X c		
TBNK c		X c,e	X c,e	X c	X c	X c		X c	X	
Imaging		X e,f			X a,m,n			X m,n	X m,n	
ECG		X								
Clinic-based Flexible nasopharyngolaryngoscopy and/or tracheoscopy with Derkay score	X f		X c,e	X i	X j	X k		X c	X m	X
Voice Handicap Index-10			X c	X c	X c	X c		X c	X	X
Exam under anesthesia with biopsies and possible debulking			X h	X i		X k			X l	
Research Blood c		X c	X c	X c	X c	X		X c	X	X
Adverse Events c				X c	X c	X		X c	X	X d
Concomitant Medications c		X c	X c	X c	X c	X		X c	X	
Leukapheresis			X h	X i						
Avelumab			X	X	X			X		X

a End of Treatment studies will be performed 42 days (+/- 10 days) after the final Avelumab treatment.

b Complete H&P at baseline, directed H&P if clinically indicated before each dose (may include clinic-based flexible nasopharyngolaryngoscopy and/or tracheoscopy), directed H&P at response assessment.

c These procedures must be performed within 3 days before each dose of avelumab while on treatment.

- d Adverse events will be followed until return to baseline or stabilization of event.
- e If the screening and baseline tests were performed prior to 3 days before the first dose of avelumab they will need to be repeated before the start of treatment. Refer to section **2.2** for screening evaluation timing requirements.
- f Within 14 days prior to subject enrollment
- g Within 28 days prior to subject enrollment
- h Within 7 days prior to first dose of avelumab
- i 9-17 days after first dose of avelumab and before second dose of avelumab
- j 9-17 days after second dose of avelumab and before third dose of avelumab
- k 9-17 days after third dose of avelumab and before the Course 2 Cycle 1 Day 1 dose, if applicable
- l 9-17 days after last dose of avelumab
- m +/- 10 days
- n If imaging is used for response assessment
- o Tests performed for End of Course 1 time point that were completed within 7 days prior to the Course 2 Cycle 1 Day1 dose of avelumab do not need to be repeated for Course 2 Cycle 1 Day 1.
- p within 90 days prior to subject enrollment
- q Patients who experience a complete response or partial response will be evaluated every 6 weeks x 3, then every 12 weeks x 3, then every 26 weeks x 2 (+/- 10 days for each time point during the first two years) or until disease progression. After completing the first 2 years' worth of follow up clinic visits, patients will be contacted annually (+/- one month) for 3 years (a total of 5 years follow up) via phone or email for patient status, dates of disease recurrence and interventions to treat recurrent disease. The first follow-up visit, which occurs 42 days (+/- 10 days) after last study treatment, will satisfy safety visit requirements as noted in section **3.6**. If unwilling or unable to travel to the NIH Clinical Center for follow-up visits, patients will be contacted by telephone regarding their status, and may be asked to send labs and physical exam reports to fulfill visit requirements.
- r Patients who do not experience a response to treatment will be contacted annually (+/- one month) for 2 years following the last dose of the study drug to document additional disease recurrence and treatments that they have received. For the safety follow-up visit which should occur approximately 42 days (+/- 10 days) after last study treatment (as noted in section **3.6**), if unwilling or unable to travel to the NIH Clinical Center, patients will be contacted by telephone regarding their status, and may be asked to send labs and physical exam reports to fulfill end of treatment safety follow-up visit requirements. Annual follow-up contact may occur via telephone.
- s As indicated in section **9.3**, all subjects will be offered the opportunity to complete an NIH advance directives form. This should be done preferably at baseline but can be done at any time during the study as long as the capacity to do so is retained. The completion of the form is strongly recommended, but is not required.

### **3.6 CRITERIA FOR REMOVAL FROM PROTOCOL THERAPY AND OFF STUDY CRITERIA**

Prior to documenting removal from study, effort must be made to have all subjects complete a safety visit approximately 42 days (+/- 10 days) following the last dose of study therapy.

#### **3.6.1 Criteria for removal from protocol therapy**

Patients will be taken off treatment for the following:

- Completion of protocol therapy
- Participant requests to be withdrawn from active therapy
- The patient receives any other treatment for RRP or requires the use of any corticosteroids (> 10 mg daily prednisone equivalents) or other immunosuppressive medications.
- General or specific changes in the patient's condition render the patient unacceptable for further treatment on this study in the judgment of the investigator.
- Any Grade 3/4 drug-related adverse events with the exceptions as detailed in section 3.4.
- Disease progression
- Participant becomes pregnant

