### 3.4.2 Resuming treatment

Subjects may resume treatment with avelumab under any of the following circumstances:

- Any grade 2 event that resolves to grade 1 or less within 14 days without systemic steroid treatment
- Grade 3/4 rash that improves to Grade 1/2 with treatment
- Grade 2/3/4 endocrinopathy that responds to treatment/replacement therapy

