#### 14.3.1 Gastrointestinal irAEs

Gastrointestinal irAEs		
Severity of Diarrhea / Colitis (NCI-CTCAE v4.03)	Management	Follow-up
Grade 1 Diarrhea: < 4 stools/day over Baseline Colitis: asymptomatic	Continue avelumab therapy Symptomatic treatment (for example, loperamide)	Close monitoring for worsening symptoms Educate subject to report worsening immediately If worsens: Treat as Grade 2 or 3/4
Grade 2 Diarrhea: 4 to 6 stools per day over Baseline; IV fluids indicated < 24 hours; not interfering with ADL Colitis: abdominal pain; blood in stool	Delay avelumab therapy Symptomatic treatment	If improves to Grade 1: Resume avelumab therapy If persists > 5 to 7 days or recur: 0.5 to 1.0 mg/kg/day methylprednisolone or equivalent When symptoms improve to Grade 1, taper steroids over at least 1 month, consider prophylactic antibiotics for opportunistic infections, and resume avelumab therapy per protocol. If worsens or persists > 3 to 5 days with oral steroids: Treat as Grade 3 to 4
Grade 3 to 4 Diarrhea (Grade 3): ≥ 7 stools per day over Baseline; incontinence; IV fluids ≥ 24 hrs; interfering with ADL Colitis (Grade 3): severe abdominal pain, medical intervention indicated, peritoneal signs Grade 4: life-threatening, perforation	Discontinue avelumab therapy per protocol 1.0 to 2.0 mg/kg/day methylprednisolone IV or equivalent Add prophylactic antibiotics for opportunistic infections Consider lower endoscopy	If improves: Continue steroids until Grade 1, then taper over at least 1 month If persists > 3 to 5 days, or recurs after improvement: Add infliximab 5 mg/kg (if no contraindication), Note: Infliximab should not be used in cases of perforation or sepsis

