14.3.2 Dermatological AEs

Dermatological AEs		
Grade of Rash (NCI-CTCAE v4)	Management	Follow-up

Grade 1 to 2            Covering ≤ 30% body surface area
	
Symptomatic therapy (for example, antihistamines, topical steroids)            Continue avelumab therapy
	
If persists > 1 to 2 weeks or recurs:            Consider skin biopsy            Delay avelumab therapy            Consider 0.5 to 1.0 mg/kg/day methylprednisolone IV or oral equivalent. Once improving, taper steroids over at least 1 month, consider prophylactic antibiotics for opportunistic infections, and resume avelumab therapy            If worsens:            Treat as Grade 3 to 4

Grade 3 to 4            Covering > 30% body surface area; life threatening consequences
	
Delay or discontinue avelumab therapy            Consider skin biopsy            Dermatology consult            1.0 to 2.0 mg/kg/day methylprednisolone IV or IV equivalent
	
If improves to Grade 1:            Taper steroids over at least 1 month and add prophylactic antibiotics for opportunistic infections            Resume avelumab therapy

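### Section 3.6.1 takes off treatment any patient needing more than 10 mg/day prednisone equivalents, yet six Appendix C rows resume avelumab after methylprednisolone 0.5-2 mg/kg/day

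*Combined protocol and SAP*

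**What the plan says.** Section 3.6.1 lists the reasons for taking a patient off treatment. One bullet covers a patient who receives another RRP treatment or "requires the use of any corticosteroids (> 10 mg daily prednisone equivalents) or other immunosuppressive medications". It has no exception. A separate bullet does have one: "Any Grade 3/4 drug-related adverse events with the exceptions as detailed in section 3.4".

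Section 3.4.2 gives three circumstances in which avelumab may be restarted:
- For moderate events in general, the condition is "Any grade 2 event that resolves to grade 1 or less within 14 days without systemic steroid treatment".
- Severe skin reactions have their own line, which reads "Grade 3/4 rash that improves to Grade 1/2 with treatment".
- Hormonal events are covered by a third line, namely "Grade 2/3/4 endocrinopathy that responds to treatment/replacement therapy".

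Appendix C takes a different line. For Grade 2 diarrhea/colitis that persists or recurs, 14.3.1 gives "0.5 to 1.0 mg/kg/day methylprednisolone or equivalent" and, after improvement to Grade 1, says to "taper steroids over at least 1 month, consider prophylactic antibiotics for opportunistic infections, and resume avelumab therapy per protocol". For a Grade 1-2 rash that persists or recurs, 14.3.2 says "Consider 0.5 to 1.0 mg/kg/day methylprednisolone IV or oral equivalent. Once improving, taper steroids over at least 1 month", followed by resumption. Four further rows have the same sequence of steroid, taper and restart.

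Appendix C is operative: 3.4.1 sends the investigator to the toxicity algorithms, although it cites Section 12.3 and they are in 14.3. Separately, the 3.4.4 table counts corticosteroids among the symptomatic treatments for a Grade 2 infusion reaction and then resumes the infusion at a reduced rate.

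**The concern.** When a patient recovers from a steroid-treated immune event, one page removes the patient and another re-doses. No text says which takes precedence. Whether someone is re-exposed to avelumab after, say, pneumonitis or a severe rash then depends on the page consulted. The opposite error is also possible: a patient whom 3.4.2 allows to restart could lose the remaining doses. Either choice could be recorded as a protocol deviation.

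**Working it through.** The plan states no figure on this point, so the check compares the texts and adds a dose conversion.

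**1. Rows that give methylprednisolone and then resume avelumab**

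| Appendix C row | Dose, mg/kg/day | Against 3.6.1 | Against 3.4.2 |
|---|---|---|---|
| 14.3.1 Grade 2 diarrhea/colitis | 0.5-1.0 | conflict | conflict |
| 14.3.2 Grade 1-2 rash, persistent (steroid only to be considered) | 0.5-1.0 | conflict if given | conflict if Grade 2 and given |
| 14.3.2 Grade 3-4 rash | 1.0-2.0 | conflict | restart permitted |
| 14.3.3 Grade 2 pneumonitis | 1.0 | conflict | conflict |
| 14.3.4 Grade 2 hepatic | 0.5-1 | conflict | conflict |
| 14.3.6 symptomatic endocrinopathy | 1-2 | conflict | restart permitted |

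That is six rows in five tables. The suspected-myocarditis row (14.3.5) is not counted because it names no steroid. The adrenal-crisis row (14.3.6) is not counted because it gives no restart step of its own.

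**2. Do these doses pass the 3.6.1 limit?** Daily prednisone equivalent = weight × mg/kg × conversion factor. The documents give no factor; I assume 1.0 to 1.25. The weight at which a dose equals 10 mg/day is 10 / (dose × factor):
- 0.5 mg/kg: 10/0.5 = 20 kg (factor 1.0) or 10/0.625 = 16 kg (factor 1.25).
- 1.0 mg/kg: 10 kg or 8 kg.

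At an assumed 70 kg, 0.5 mg/kg is 35-44 mg/day and 2 mg/kg is 140-175 mg/day. Entry requires age 18 or over, so every adult dosed under these rows is above the limit.

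**3. The 3.4.2 conflict.** It rests on the steroid-free condition. The 14-day limit there concerns resolution of the event, not the length of the taper, so the taper of at least one month is not itself a breach of 3.4.2.

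**4. Conflict within the main text.** 3.4.2 allows restart after treated Grade 3/4 rash and endocrinopathy, and 3.4.4 allows the infusion to resume after a Grade 2 reaction. The 3.6.1 exception for section 3.4 is on the adverse-event bullet, so it does not protect these patients if they received steroids above the limit.

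**5. How many patients.** Section 12.1.4 (717 subjects) puts rash, hypothyroidism, AST increased and ALT increased each at 2% to below 5%, any grade. Assuming these rates carry over to RRP:
- 37 patients: 37 × 0.02 = 0.74 to below 37 × 0.05 = 1.85 per event type.
- 40 patients: 0.8 to below 2.0.

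Diarrhea is among the most frequent events there, but its rate is given only as at least 2%. Pneumonitis is not in the list. Only the steroid-treated subset meets the conflict, and its rate is not given.

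**6. Doses at stake after an event at dose 1.** Course 1: 3 - 1 = 2. Both courses: 6 - 1 = 5, but 3.1.1 gives Course 2 only to partial responders at week 6. A taper of at least 28 days spans at least 28/14 = 2 dosing intervals.

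**7. Simon design.** Early termination under the null is 0.95^12 = 0.540, as stated in section 9. With the 0/12 and 3/37 boundaries, alpha is 0.093 and power 0.902. No re-dosing rule enters these figures.

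**The case against.** The best defence reads the steroid bullet as a continuing need. On that reading a patient is off treatment while on more than 10 mg/day, and Appendix C restarts only after improvement and taper. Section 3.4.3 supports this to a degree, since it reserves permanent discontinuation for Grade 3/4 drug-related events. The 3.4.4 infusion-reaction rule also suggests that 3.6.1 was not meant to remove everyone ever given a steroid. The reading is possible, so the conflict with 3.6.1 is less certain than the bare wording suggests. It is not decisive. Most neighbouring bullets in 3.6.1 (completion, progression, pregnancy) are terminal, and the reading does nothing for the Grade 2 rows, because 3.4.2 excludes steroid-treated Grade 2 events in its own terms.

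A reader might also infer that stopping avelumab satisfies every section, so that nothing needs repair. The documents do not support that. 3.4.2 is permissive, the Grade 3-4 rash row offers delay or discontinuation, and the diarrhea/colitis row defers to the protocol. The pneumonitis, hepatic and endocrine rows have no such qualifier and simply direct resumption.

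It is also fair that the rash conflict with 3.4.2 is conditional. 3.4.1 does not delay dosing for Grade 2 rash, the appendix only suggests steroids, and 3.4.2 is silent on Grade 1.

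**Conclusion.** The inconsistency is real and worth correcting, at low priority. Six rows conflict with 3.6.1 as written. Three of them, or four when a Grade 2 rash is given steroids, also conflict with 3.4.2. For Grade 3/4 rash, endocrinopathy and the steroid-treated Grade 2 infusion reaction, the clash lies within the main text.

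Two stronger readings should be resisted. One is that four rows conflict with 3.4.2 unconditionally; the rash row does so only for a Grade 2 rash that actually receives steroids. The other is that affected patients generally forfeit 5 of 6 doses. That figure needs an event after dose 1 in a patient who would have reached Course 2 as a partial responder; otherwise the most at stake is 2 of 3.

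The dose conclusion is insensitive to the assumed conversion factor. The patient count rests on the carry-over of solid-tumor rates and on an unknown steroid-treated fraction, so few patients or none is as far as the documents go. The sample size, boundaries and error rates stand.

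**What to change.** 1. **Appendix C.** In the Grade 2 diarrhea/colitis, pneumonitis and hepatic rows, and for steroid-treated Grade 1-2 rash, replace resumption after steroids with an instruction not to resume if systemic steroids were required, citing 3.4.2 and 3.6.1. This makes steroid-treated Grade 2 rash stricter than treated Grade 3/4 rash. If the sponsor does not want that, it can add steroid-treated Grade 1-2 rash to the exceptions in step 2.
2. **Section 3.6.1.** Add to the steroid bullet an exception for events that section 3.4 already lets restart: Grade 3/4 rash and Grade 2-4 endocrinopathy, once steroids are down to 10 mg/day prednisone equivalents or less (the limit also used in exclusion 2.1.2.3), and short-course corticosteroids for a Grade 2 infusion reaction managed under 3.4.4. For Grade 3/4 rash, keep the stricter 14.3.2 threshold of improvement to Grade 1, rather than the Grade 1/2 of 3.4.2, unless the sponsor decides otherwise.
3. **Precedence.** State that 3.4 and the amended 3.6.1 govern over Appendix C on re-dosing, apart from that rash threshold. Correct the 3.4.1 cross-reference from 12.3 to 14.3.

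The cost is a wording amendment, with no change to visits, sample size or boundaries. The downside is that an occasional patient given steroids for an event in step 1 loses the remaining doses, which 3.6.1 read literally already requires.

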#### **3.6.2 Duration of Follow up**

Patients who do not experience a complete response will be contacted annually for two years after the 42 day (+/- 10 days) follow up visit to determine the date of disease recurrence following completion debulking on this study and the dates and types of additional interventional procedures to control RRP. Patients who experience a complete response will be contacted annually for three years after completing the first 2 years' worth of follow up clinic visits (for a total of approximately five years of follow up). The dates of disease recurrence and interventions to treat recurrent disease will be recorded.

#### **3.6.3 Off-Study Criteria**

Patients will be taken off study for the following:

- The patient voluntarily withdraws
- There is significant patient noncompliance
- The investigators decide it is in the patient's best interest
- The patient completes follow-up
- Death

### **3.7 STOPPING RULE**

3.7.1 All protocol treatment will be temporarily stopped to allow for review of data and consultation with the FDA and IRB if either of the following events occur:

- Any treatment-related death
- Three  $\geq$  Grade 3 Unexpected Serious Adverse Events

3.7.2 All protocol treatment will be temporarily stopped to allow review of interim summary of safety and efficacy following completion of the pilot cohort prior to expanding enrollment.

#### **4 BIOSPECIMEN COLLECTION**

Biospecimen collection on this protocol will consist of blood draws, leukapheresis products, and biopsies of papillomas and adjacent tissue.

##### **4.1 CORRELATIVE STUDIES FOR RESEARCH**

###### **4.1.1 Biospecimen collection before the start of avelumab**

- Patients will also be invited to enroll on protocol 16C0061 for which patients must consent separately.
- Blood will be collected for research purposes. A total of 12 CPT tubes (8 mL each of blood) will be collected prior to the first dose of avelumab. This is a total of 96 mL of blood. This blood will be used for immunology assays. This blood can be collected on different days as long as a total of 12 CPT tubes are collected prior to the first dose of avelumab. One CPT tube will be used to collect plasma which will be frozen in a 4mL vial. PBML from the remainder of the CPT tubes will be frozen in aliquots of  $10 \times 10^6$  cells/vial. Send to ETIB's Pre-Clinical Core lab; Attention [name], [name] contact [contact].
- 16 mL of blood will be drawn to obtain serum for research purposes (2 SST tubes, 8 mL per tube) within 14 days prior to the first dose of avelumab. This will be processed in ETIB Pre-Clinical Core and frozen in aliquots of 0.5-1mL/vial. Send to ETIB's Pre-Clinical Core lab; Attention [name], [name] contact [contact].
- A research apheresis sample will be collected prior to first dose of avelumab. Apheresis collection will be 5 L volume (as close to 5 L as possible). Apheresis will only be performed on patients with adequate peripheral venous access. Cells will be transferred to ETIB 's Pre-Clinical Core lab, Attention [name], [name], contact [contact]. Aliquots of PBMC and plasma will be cryopreserved for immunological monitoring. Cell product will be frozen in 10 vials at concentration  $100 \times 10^6$  cells/mL and additional vials at  $300 \times 10^6$  cells/mL. Papilloma and adjacent tissue samples will be collected by biopsy prior to the first dose of avelumab. Biopsies will be obtained with rigid or flexible endoscopy under sedation or general anesthesia. They will consist of up to 10 papilloma fragments, each 1-3 mm in diameter. One fragment may be sent to pathology for permanent sections. The other fragments of the biopsy will be sent to [name] laboratory in sterile 1.5 mL Eppendorf tubes with a small amount of sterile normal saline. Additional tissue that is removed to debulk papillomas may also be collected for research. Up to two fragments of normal mucosa, each 1-3 mm in diameter, will also be obtained and sent to [name] laboratory. Send to [name] lab; [name].

- Patients with papillomas that cannot be biopsied by endoscopy may participate in the trial. All tissue specimen collection except papilloma biopsies will be performed.
- Specimens will be cataloged and stored in ETIB's Pre-Clinical Core lab. Assays will be performed retrospectively.

#### 4.1.2 Biospecimen collection during treatment and follow-up

- Patients will return to the Clinical Center every two weeks for avelumab dosing. Blood and serum for research and TBNK testing will be obtained prior to each dose of avelumab. Blood for research will consist of:
  - 6 CPT tubes of Research Blood (48 mL) will be collected for immunological testing and processed as described in section 4.1.1. Attention [name], [name] contact [contact].
  - 1 SST tube (8 mL) of Research Blood will be obtained for serum collection and processed as described in section 4.1.1 . Attention [name], [name] contact [contact].
- Papilloma and adjacent tissue samples will be collected by biopsy 2 weeks after the first dose of avelumab (9-17 days after the first dose). This should occur prior to second dose of avelumab. Repeat biopsies will be collected again two weeks after the third dose of avelumab (9-17 days after the third dose), which corresponds to the end of the first course (3 doses) of avelumab. These procedures should occur before Course 2, if applicable. Biopsies will again be collected at the time of completion debulking for patients who do not experience a complete tumor response. Biopsies will be obtained with rigid or flexible endoscopy under sedation or general anesthesia. They will consist of up to 10 papilloma fragments, each 1-3 mm in diameter. One fragment may be sent to pathology for permanent sections. The other fragments of the biopsy will be sent to [name] laboratory in sterile 1.5 mL Eppendorf tubes with a small amount of sterile normal saline. Up to two fragments of normal mucosa, each 1-3 mm in diameter, will also be obtained and sent to [name] laboratory. Send to [name] lab; [name]; Attention: [name] [contact].
- A research apheresis sample will be collected 2 weeks after the first dose of avelumab (9-17 days after the first dose). This apheresis should occur before the second dose of avelumab. Apheresis will only be performed on patients with adequate peripheral venous access. Cells will be transferred to ETIB 's Pre-Clinical Core lab, Attention [name], [name], contact [contact]. Aliquots of PBMC and plasma will be cryopreserved for immunological monitoring. Cell product will be frozen in 10 vials at concentration 100 x10^6 cells/mL and additional vials at 300 x 10^6 cells/mL.If patients experience a complete response, they will continue to be followed every 6 weeks x 3, then every 12 weeks x 3, then every 26 weeks x 2. Research blood and TBNK will be collected at these time points as described above.

